5.6.2. Analysis of Secondary Efficacy Variables

All secondary endpoints will be analyzed descriptively at given visits. SAF will be used for efficacy analysis at week 24, and subset of SAF at week 36 will be used for efficacy analysis at week 36.

Continuous Endpoint at week 24

The change from baseline to week 24 in the cumulative tolerated dose (log transformed) of peanut protein during a DBPCFC will be summarized descriptively. Estimate of change from baseline to week 24 and the 2-sided 95% confidence interval will be provided. If patients do not tolerate any dose level of peanut protein challenge, they will be assigned a cumulative tolerated dose of 1 mg prior to converting to the log scale.

Missing data for week 24 DBPCFC will be handled according to the reason for missingness as follows:

• If a patient misses the week 24 DBPCFC due to COVID-19, the missing data will be imputed by MI method for 10 times utilizing available week 24 DBPCFC data. The MI will utilize logistic regression method with baseline tolerated cumulative amount of peanut protein DBPCFC.

Protocol: R668-ALG-1702

Date: March 3, 2021

• If a patient does not have an available week 24 DBPCFC due to reasons not related to COVID-19, the baseline value at screening DBPCFC will be used to impute the missing week 24 DBPCFC data.

Each of the complete datasets after the above steps will be summarized with estimated means and standard errors of change from baseline to week 24 in the cumulative tolerated dose (log transformed) of peanut protein. The SAS MIANALYZE procedure will be used to generate valid statistical inferences by combining results.

Supportive analysis will include an analysis of patients who have available week 24 DBPCFC of peanut protein.

Binary Endpoint at week 24

For the below binary endpoints of passing a DBPCFC at week 24, the analysis and imputation methods will be similar to the primary analysis.

- Proportion of patients treated with dupilumab that pass a DBPCFC with at least 1044 mg (cumulative) peanut protein at week 24
- Proportion of patients treated with dupilumab that pass a DBPCFC with at least 2044 mg (cumulative) peanut protein at week 24

Proportion of patients with Grade II or above allergic reactions during the DBPCFC at week 24 will summarized descriptively as well as proportion of patients using ephinephrine as a rescue medication during the DBPCFC at week 24.

Continuous Endpoint at week 36

Change in the cumulative tolerated dose (log transformed) mg of peanut protein during a DBPCFC from baseline to measured DBPCFC at week 36 will be summarized descriptively based on a subset of SAF at week 36.

Binary Endpoints at Week 36

Proportion of patients treated with dupilumab that pass a DBPCFC with at least 444 mg (cumulative) peanut protein at week 36 will be summarized descriptively based on a subset of SAF at week 36. Similar binary endpoints at week 36 will be summarized in a similar fashion.

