11.4.3.2. Secondary Efficacy Analysis

All secondary endpoints (Section 4.1.2) will be analyzed descriptively at given visits. FAS will be used for efficacy analysis at week 24, and week 36 FAS will be used for efficacy analysis at week 36.

All secondary endpoints will be analyzed descriptively at given visits. FAS will be used for efficacy analysis at week 24, and week 36 FAS will be used for efficacy analysis at week 36. For binary endpoints, the analysis and imputation methods will be similar to the primary analysis.

A one-sample t-test will be performed to assess the change from baseline to week 24 in the cumulative tolerated dose (log transformed) of peanut protein during a DBPCFC. Estimate of change from baseline to week 24, p-value, and the 2-sided 95% confidence interval will be provided. If the data is extremely skewed, nonparametric method may be applied. Details will be provided in the SAP. The missing data will be imputed by the last non-missing DBPCFC assessment including baseline.

For other continuous endpoints, the analysis and imputation methods will be applied similarly.

Sensitivity analysis will include an analysis based on the observed cases. Other sensitivity analysis may be proposed in the SAP.

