2.3. Sample Size and Power Considerations

The sample size is determined to adequately power the primary endpoint of the proportion of patients who pass at least a DBPCFC of 444 mg (cumulative) of peanut protein at week 24. Based on assessment of clinical data from Aimmune Therapeutics AR101 phase 3 peanut OIT study (ARC003), it is assumed that the rate of a tolerated cumulative dose of at least 444 mg of peanut protein on DBPCFC at week 24 is 8% in placebo (Vickery, 2018) and 29% in dupilumab.

A sample size of 20 patients will have 80% power to detect the 21% difference in tolerated rate at the 2-sided 5% significance level. Allowing for a dropout rate of around 15%, approximately 24 patients will be required. The sample size calculations were done by one-sample Chi-square test (normal approximation) using nQuery + nTerim 4.

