5.3. Prior and Concomitant Medications/Procedures

Number and proportion of patients taking prior/concomitant medications, prohibited medications and rescue medications will be summarized for study total based on the SAF by ATC level 2 and ATC level 4, sorted by decreasing frequency of ATC level 2 and ATC level 4 based on the overall incidence. Patients will be counted only once for each medication class (ATC levels 2 and 4) linked to the medication.

Number and proportion of patients taking prior/concomitant procedures will be summarized for study total based on the SAF, sorted by decreasing frequency of SOC and PT based on the overall incidence. Patients will be counted only once for each SOC and PT linked to the procedure.

In addition, the summary of prior/concomitant medications/procedures will be performed for patients who were impacted by COVID-19 pandemic and not impacted by COVID-19 pandemic, respectively. The summary will be performed for pre-, during, and post-COVID-19 periods for patients impacted by COVID-19 pandemic, if applicable.

Number and proportion of patients taking at least one epinephrine for treatment of acute-allergic reactions will be summarized during the following periods,

- Screening DBPCFCs of peanut protein
- Week 24 DBPCFCs of peanut protein
- Week 36 DBPCFCs of peanut protein

Kaplan-Meier curves for time to first rescue treatment use will be created.

Listing of pre-treatment and concomitant medications will include generic name, ATC levels 2 and 4, indication, the study day of onset (for medications started before treatment, the study day of onset = date of medication start – date of the first dose; for medication started on or after treatment, the study day of onset = date of medication start – date of the first dose + 1), the study day of medication end date, ongoing status, dose, frequency, and route.

Protocol: R668-ALG-1702

Date: March 3, 2021

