5.6. Analyses of Efficacy Variables

The primary efficacy analyses for all the efficacy endpoints will be conducted at week 24 using the SAF population. The continuous efficacy variables will be summarized using number of patients, mean, SD, minimum, median, Q1, Q3 and maximum. The categorical efficacy variable will be summarized using patient count and proportion. The analyses of efficacy variables are described in the subsections below and summarized in Section 10.1.

Protocol: R668-ALG-1702

Date: March 3, 2021

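### Week 24 rates of Grade II+ reactions and epinephrine use default to all treated patients, with no challenged-patient denominator, which would understate them if anyone misses the challenge

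*SAP*

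**What the plan says.** **Population.** SAP 3.1 defines the SAF as every patient who received any dupilumab; having had a challenge is not required. SAP 5.6 states: "The primary efficacy analyses for all the efficacy endpoints will be conducted at week 24 using the SAF population". It adds that categorical variables are shown as a count and a proportion. SAP 5.6.2 repeats the SAF for week 24. SAP 4.5.2 lists Grade II+ reactions and epinephrine use during the week 24 challenge as secondary efficacy endpoints, so the SAF is their default population.

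**Rule for the two endpoints.** SAP 5.6.2 reads: "Proportion of patients with Grade II or above allergic reactions during the DBPCFC at week 24 will summarized descriptively". The same sentence covers epinephrine use. It gives no denominator and does not say how to treat a patient without a challenge. The SAP's imputation rule for binary endpoints is confined to those of passing the challenge. The available-data supportive analyses are attached to the primary endpoint and to the log-dose change. Section 10.1 lists neither harm endpoint.

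**Protocol.** Section 11.4.3.2 is broader: "For binary endpoints, the analysis and imputation methods will be similar to the primary analysis". In the primary analysis, a missing challenge makes the patient a non-responder.

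**Related summaries.** SAP 5.3 says: "Number and proportion of patients taking at least one epinephrine for treatment of acute-allergic reactions will be summarized during the following periods". The periods are the screening, week 24 and week 36 peanut challenges. SAP 5.7.2 asks for percentages of patients with anaphylaxis during challenges. Neither section restricts the denominator to patients challenged at that visit.

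**The concern.** A patient who is never challenged cannot react to the challenge or need epinephrine during it. Keeping that patient in the denominator lowers the rate without adding information about how severe the reactions are. For the passing endpoints, counting a missing challenge as a failure is conservative. For a harm endpoint, a patient with no possible event pulls the result in the favourable direction.

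The plan expects some missed challenges. The sample size allows for around 15% dropout, and Protocol 7.4 rules out replacement. The individual stopping rules in Protocol 6.1.3.1 cover the food challenge as well as the drug, and SAP 5.6.1 has a rule for challenges missed because of COVID-19. The stopping reasons include severe allergic reactions and poorly controlled atopic disease, so the patients without a challenge may not be a random subset.

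These two proportions are the secondary endpoints that show how severe challenge reactions are on treatment. If the denominator is not fixed in advance, it can also be chosen after the data are seen.

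**Working it through.** **1. The plan's own figures.** The documents give no figure for either harm endpoint, so the sample size is the only anchor. Inputs from SAP 2.3: "A sample size of 20 patients will have 80% power"; the rate "is 8% in placebo (Vickery, 2018) and 29% in dupilumab"; two-sided 5% level; one-sample chi-square test by normal approximation.

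n = [(z0.975·√(p0(1−p0)) + z0.80·√(p1(1−p1))) / (p1−p0)]²

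= [(1.960·√(0.08·0.92) + 0.842·√(0.29·0.71)) / 0.21]² = 18.93, so 19. Power at n = 20 is 81.5%.

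On dropout, the SAP says: "Allowing for a dropout rate of around 15%, approximately 24 patients will be required". 20/(1−0.15) = 23.5, so 24. Both planning figures reproduce. They give a working case of 24 treated and 20 challenged. This treats the dropout allowance as missed challenges, which is an assumption.

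**2. Size of the dilution.** Let N be the number in the SAF, C the number challenged and x the number of challenged patients with the event.

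- Rate among challenged = x/C
- Rate over the SAF = x/N = (x/C)·(C/N)
- Relative understatement = 1 − C/N, whatever x is

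At C = 20: 1 − 20/24 = 16.7%. At C = 22: 1 − 22/24 = 8.3%. At C = 24: zero.

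**3. Illustrations.** N = 24; the event counts are assumed.

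| Challenged | Events | Among challenged | Over SAF | Difference (points) |
|---|---|---|---|---|
| 20 | 5 | 25.0% | 20.8% | 4.2 |
| 20 | 10 | 50.0% | 41.7% | 8.3 |
| 20 | 15 | 75.0% | 62.5% | 12.5 |
| 22 | 10 | 45.5% | 41.7% | 3.8 |
| 24 | 10 | 41.7% | 41.7% | 0 |

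For 10 events and 20 challenged, the Clopper-Pearson 95% intervals are 27.2% to 72.8% among challenged and 22.1% to 63.4% over the SAF.

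**4. What the missing rule could do.** If the four unchallenged patients were instead counted as events, 10 events would become 14/24 = 58.3%. The same data could therefore be reported as 41.7%, 50.0% or 58.3%, depending on a rule that the SAP does not state for these endpoints.

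**The case against.** A reader might infer that the plan scores unchallenged patients as event-free. The documents do not say that. The SAP names an analysis population but does not write out the denominator of these two proportions, and a descriptive summary could be computed among patients with data. Nor does the SAP impute here, because its rule covers only the passing endpoints. The broader protocol sentence does not define what a non-responder would mean for a harm, and Protocol 11 describes itself as the basis for the SAP, which is the more specific text. All of this stands, so the point concerns the consequence of the default population and not a written rule.

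A second tempting step is to present the week 36 epinephrine summary as the worst case, since only week 24 passers are challenged then. Epinephrine use is a secondary endpoint at week 24 only. The SAP already uses a restricted subset for week 36 efficacy, and its sentence on epinephrine by challenge period can be read as referring to those challenged. SAP 5.3 still needs an explicit denominator, but a week 36 rate over the full SAF is not an established plan.

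It is also fair to say that the study has one arm and these endpoints are not tested, that disposition is reported with reasons, and that a reader given both counts could compute either proportion. Patients who stop drug but remain in the study are asked to attend the remaining visits (Protocol 8.3.2), so fewer than four of 24 may miss the challenge. These points limit the consequence.

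They do not remove the default. Where the SAP wants observed data, it says so: for the supportive analyses in 5.6.1 and 5.6.2 and for biomarkers in 5.11. No such wording covers these two endpoints, so a programmer following the text would divide by the SAF.

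**Conclusion.** The concern holds as a problem with the default denominator. Followed as written, the SAP puts both harm proportions on the SAF, and each is then understated by exactly the fraction of treated patients not challenged. That is 16.7% in relative terms at 20 of 24, 8.3% at 22 of 24, and nothing if all are challenged. The size rests on two assumptions: that SAF patients without a challenge remain in the denominator with no event, and that the planning figures approximate the number challenged. The relative figures do not depend on the event count; the percentage-point examples do.

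The documents do not support the stronger statement that the plan classifies these patients as event-free, or that the reported rates will certainly be too low. The primary endpoint and the sample size are unaffected.

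**What to change.** In SAP 5.6.2, define both proportions among SAF patients who received at least one peanut-day dose at the week 24 challenge. Report the number not challenged, state that nothing is imputed for these endpoints, and show the SAF-based figure only as supplementary. Add both endpoints to Section 10.1 with that denominator.

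Use the same visit-specific challenged denominator for the epinephrine summaries in 5.3, including the descriptive one at week 36, and for the challenge anaphylaxis summary in 5.7.2.

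The cost is a few sentences and two table rows, with no new data. The reported reaction rates become slightly less favourable if any patient misses the challenge. A rate among challenged patients also does not correct for selective missingness, which is why the number not challenged belongs beside it.

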5.6.3. Analysis of Exploratory Efficacy Analysis

The analysis of other efficacy variables will be the same as the primary analysis described in Section 5.6.1 and Section 5.6.2.

5.6.4. Adjustment for Multiple Comparison

No adjustments for multiplicity for the secondary endpoints are planned for this study.

5.6.5. Subgroup Analysis

Subgroup analysis for the primary endpoint and the following secondary endpoints will be performed on the SAF. Subgroups are defined in the Section 3.4.

• Change in the cumulative tolerated dose (log transformed) mg of peanut protein during a DBPCFC from baseline to measured DBPCFC visits at week 24

Protocol: R668-ALG-1702

Date: March 3, 2021

- Proportion of patients treated with dupilumab that pass a DBPCFC with at least 1044 mg (cumulative) peanut protein at week 24
- Proportion of patients treated with dupilumab that pass a DBPCFC with at least 2044 mg (cumulative) peanut protein at week 24

The analysis method for the subgroup analysis will be the same as the primary analysis described in Section 5.6.1 and Section 5.6.2.

5.7. Analysis of Safety Data

The analysis of safety and tolerance will be performed on the SAF, as defined in Section 3.1.

The safety analysis will be based on the reported AEs and clinical laboratory evaluations, physical examination, vital signs and spirometry.

Thresholds for treatment-emergent Potential Clinically Significant Values (PCSV) in laboratory variables and vital signs are defined in Section 10.3. Treatment-emergent PCSV is any PCSV developed or worsened in severity compared to the baseline during the treatment and follow-up period. The baseline when determining treatment-emergent PCSV refers to the baseline value of the study.

The time interval to detect any event or abnormality is between the first injection of study medication and EOS.

5.7.1. Adverse Events

The number and proportion of patients reporting TEAEs will be summarized for treatment period and follow-up period separately, as described in Section 3.1.

AE incidence tables will be presented for the SAF as well as subgroups. Summary of TEAEs will present the number (n) and percentage (%) of patients experiencing an TEAE by SOC and PT, sorted by the decreasing frequency of SOC and PT. Multiple occurrences of AEs of the same PT (or SOC) in the same patient will be counted only once for that PT (or SOC). For AE tables presenting severity, the worst severity will be chosen for patients with multiple instances of the

same event. The denominator for computation of percentage is the number of patients for the corresponding analysis period as specified in Section 3.1.

Protocol: R668-ALG-1702

Date: March 3, 2021

An overall summary of TEAEs will be provided with number and proportion of patients with any:

- TEAE
- Serious TEAE
- TEAE/Serious TEAE leading to death
- TEAE/Serious TEAE leading to permanent treatment discontinuation
- Study drug related TEAE/serious TEAE
- Maximum intensity for TEAE

Detailed summaries of TEAEs will include:

- TEAEs
 - TEAEs by primary SOC/PT
 - TEAEs by primary SOC/HLT/PT
 - TEAEs by PT
 - TEAEs by primary SOC/PT with incidence of PT \geq 5%
 - TEAEs by severity and by primary SOC/PT
 - TEAEs related to study drug as assessed by the investigator by primary SOC/PT
 - Severe TEAEs by primary SOC/PT
 - Severe TEAEs related to study drug as assessed by the investigator by primary SOC/PT
 - TEAEs leading to permanent discontinuation of study treatment by primary SOC/PT
- Serious TEAE
 - Serious TEAEs by primary SOC/PT
 - Serious TEAEs related to study drug as assessed by the investigator by primary SOC/PT
 - Time to first occurrence of serious TEAEs
- Death by primary SOC/PT

Number and proportion of patients reporting pre-treatment adverse events will be tabulated by primary SOC and PT.

The number and proportion of patients with injection site reaction by PT will be summarized.

The number and proportion of TEAE per 100 patient-year will be tabulated by primary SOC/HLT/PT. The number of patients with at least one event per 100 patient-year will be calculated and summarized for the following:

Protocol: R668-ALG-1702

Date: March 3, 2021

- TEAE by primary SOC/HLT/PT
- Severe TEAE by primary SOC/HLT/PT
- Serious TEAE by primary SOC/HLT/PT

Listing of TEAEs, serious TEAEs, and TEAEs resulting in death and study drug discontinuation will be generated. The following variables will be included in the listing:

- Patient ID
- Age/sex/race
- System Organ Class (SOC)
- High Level Term (HLT)
- Preferred Term (PT)
- Verbatim Term
- AE start date and end date/ongoing (including both calendar days and study days)
- AE duration
- Relationship of AE to study drug: Related or Not Related
- Action taken with study drug: Dose not changed, Drug interrupted, Drug withdrawn, Not applicable, or Unknown
- Severity: mild, moderate, or severe
- Outcome: Fatal, Not recovered/not resolved, Recovered/resolved, Recovered/resolved with sequelae, Recovering/resolving, or Unknown
- Impact by COVID-19 pandemic: Yes or No

In addition, summary of adverse events will be categorized by the status of impact by COVID-19 pandemic. For patients who were impacted by COVID-19 pandemic, the summary of adverse events will include overall summary of adverse event, TEAEs by SOC/PT, serious TEAEs by SOC/PT (if applicable), TEAEs of special interest (if applicable), TEAEs leading to discontinuation of study treatment by SOC/PT (if applicable). The summary of adverse events for patients who were not impacted by COVID-19 pandemic will be summarized similarly. The summary of adverse events will be performed for pre-, during-, and post-COVID-19 periods for patients impacted by COVID-19 pandemic, if applicable.

5.7.2. Analysis of Adverse Events of Special Interest

The adverse events of special interest (AESI) will be summarized by AESI category (see Section 10.4) and HLT/PT. In addition, it will be summarized by AESI category only.

Protocol: R668-ALG-1702

Date: March 3, 2021

The time to first AESIs (AESI by category) will be assessed by Kaplan-Meier estimates. Kaplan-Meier curves will be provided. The time is defined as the date of first event – date of first dose + 1. Patients without an event will be censored at the end of study visit.

The number of anaphylactic reactions, the number and percentage of patients experiencing an anaphylactic reaction, the number and percentage of patients experiencing an anaphylactic reaction by maximum severity using the Muraro Grading Scale (Muraro 2007), the number of patients experiencing an anaphylactic reaction was an SAE, the number of patients experiencing an anaphylactic reaction that required use of epinephrine will be summarized during DBPCFCs.

5.7.3. Clinical Laboratory Measurements

Laboratory measurements include clinical chemistry, hematology and urinalysis results, and will be converted to standard international units. Summaries of laboratory variables will include:

- Descriptive statistics of laboratory result and change from baseline by visit
- The number (n) and percentage (%) of patients with treatment-emergent PCSVs. This summary will be provided based on all patients in the SAF as well as in the subgroup of SAF patients who did not meet the PCSV criterion at baseline
- Shift tables based on baseline normal/abnormal and other tabular and graphical methods may be used to present the results for parameters of interest

Listing of all laboratory parameters normal ranges, abnormal flag, treatment-emergent PCSV by patient, visit and the status of impact by COVID-19 pandemic will be provided.

In addition, summaries of laboratory variables will be performed for patients who were impacted by COVID-19 pandemic and not impacted by COVID-19 pandemic, respectively. The summaries will be performed for pre-, during-, and post-COVID-19 periods for patients impacted by COVID-19, if applicable.

The graph of mean change and/or percent change from baseline value for lab parameters by visit will be provided.

